3.2 Study Outcome Measures

The primary outcome measure to determine success of treatment will be overbite at the end of treatment. Overbite will be measured in two ways. The first method is to record whether the incisors have positive overlap at the end of treatment, which indicates success. This will be judged from the frontal photographs at all three time points (baseline/enrollment, end of active treatment, and one year after end of active treatment). Second, using lateral cephalograms, the overbite will be measured relative to a standardized reference line (for example, occlusal plane), at two time points. At the first time point, we will see that relative to occlusal plane, the initial overbite is negative (no incisal overlap), and the distance between the maxillary and mandibular incisor tips can be measured in millimeters perpendicular to the occlusal plane. At the second time point, the final overbite should be positive (incisal overlap), and this overlap can be measured in millimeters perpendicular to the occlusal plane. Based on the measurements from the initial and final cephalograms, we will assess whether the overbite has been treated successfully (positive incisal overlap), as well as how much the overbite has improved (in millimeters).

The primary measure to determine stability of treatment ascertained one year after removal of orthodontic appliances is the overbite measurement. Since a cephalogram will not be taken one year after the end of treatment, this measurement will need to be assessed from the photographs. Overbite will be measured in two ways. The first is the dichotomous assessment of incisal overlap at the follow-up time; this will be performed in the same manner as stated in the preceding paragraph. A positive incisal overlap will be considered stable. The second method will be performed by utilizing the proportions of teeth in order to determine how much overbite change has occurred (see Appendix C). The orthodontist will be asked to measure the height of the right maxillary central incisor at the time of deband and at the final visit. Using this measurement, along with the end-of-treatment and follow-up photos, the overbite can be calculated at each time point, as well as the amount of overbite change.

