Secondary outcome measures to examine how retainer regimens, as well as treatment modalities, dentofacial, patient and practitioner characteristics are associated with treatment stability and patient satisfaction one year after the end of active treatment include the following:

- Treatment stability is described above for the primary objective.
- Retainer regimens include: Type (Hawley, Essix, bonded), whether full-time or part-time (nights only) and compliance with these recommended regimens (ascertained through practitioner and, separately, patient self-report).
- Patient satisfaction: Overall satisfaction with retainers (and secondarily, satisfaction with esthetics and function separately), all of which will be ascertained by patient report at one year after end of active treatment.
- Other factors of interest for each include success of treatment at end of active treatment, and as described above, dentofacial characteristics (molar class, crowding, facial pattern, magnitude (millimeters) of overbite), treatment modalities (extraction, then surgical component, fixed appliances, removable aligners, TADs), practitioner characteristics (age, race, sex, years since received orthodontic training) and patient characteristics (age, race, sex, insurance, education, treatment preference (whether agreed with primary recommendation), and treatment goal).

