11.3 Final Analysis Plan

Analysis plan for Primary Objectives:

Primary objective #1 is to estimate the proportion of patients who are successfully treated. As described in section 3.2 (outcome measures), successful treatment is defined as occurring when patients have positive overlap at the end of treatment; this will be calculated with a 95% confidence interval.

Though not an explicit hypothesis, we expect those that are “successfully” closed will have had a smaller distance between the maxillary and mandibular incisor tips prior to treatment, i.e., at enrollment, than those not successfully closed. We will calculate the mean distance improved separately for those successfully treated and those not. It may be that those not successfully treated had more improvement than those who were successfully treated (if the former had a greater distance that needed to be corrected) and we want to capture this. Thus, as an additional but secondary measure of improvement, we will also calculate mean and median distance improved as descriptive measures.

Primary objective #2 is to estimate, among patients who are successfully treated, the proportion of patients whose treatment is stable. As described in section 3.2 (outcome measures), stability will be assessed one year after end of active treatment. The primary measure (strictest, most conservative classification) will be among patients who are determined to have been successfully treated at end of active treatment (having closed their AOB), what proportion of these have positive overlap at the one-year follow up time. This proportion will be estimated with a 95% confidence interval. Additional assessments of stability will include the proportion of all who had improvement in overbite (positive increases) during retention, no change in overbite during retention, and worsening of overbite (negative increases) during retention. We will calculate these mean and median changes as descriptive measures.

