Secondary objective #3a will examine how retainer regimens, as well as treatment modalities, dentofacial, patient and practitioner characteristics are associated with treatment stability. Stability is defined above, namely, at one year after end of active treatment there is positive overbite. First, the association of retainer regimens, namely, type of retainer (Hawley, Essix, bonded) and frequency of use prescribed (full or part-time) with treatment stability will be assessed with chi-square test. The treatment modalities (extraction, then surgery, fixed appliances, removable aligners, or TADs), dentofacial, patient and practitioner characteristics described above, will be used to ascertain their association with treatment stability. The process, being domain specific, will model criteria entry if $p < 0.2$; retain at $p < 0.1$. Final model, all domains combined, entry if $p < 0.1$; retained if $p < 0.05$. For this secondary objective (3a), retainer regimens will be included, first as a domain in the same manner that treatment modalities, dentofacial, patient, and practitioner characteristics are. Then, stratum specific analyses will be performed separately according to whether or not treatment included extraction and whether or not treatment was successful (AOB closed at end of active treatment).

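### Objective 3a drops the closure condition from its definition of stability, so its main analysis implicitly mixes failure to close with relapse

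*Protocol*

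**What the plan says.** Protocol section 11.3 makes the primary stability estimate conditional on closure: "Primary objective #2 is to estimate, among patients who are successfully treated, the proportion of patients whose treatment is stable". Section 11.2 follows the same logic, inflating the number needed for the stabilization rate by the success rate.

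Section 3.2 gives the reading rule for the one-year photograph, "A positive incisal overlap will be considered stable", without naming a population. For the one-year outcomes it also says "Other factors of interest for each include success of treatment at end of active treatment".

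For objective 3a, section 11.4.2 states "Stability is defined above, namely, at one year after end of active treatment there is positive overbite" and sets this order of work:
- chi-square tests of retainer type and prescribed use;
- domain-by-domain selection, in which "retainer regimens will be included, first as a domain in the same manner that treatment modalities, dentofacial, patient, and practitioner characteristics are";
- a final model over all domains;
- separate analyses by extraction and by "whether or not treatment was successful (AOB closed at end of active treatment".

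Objective 3b then uses stability at one year as an independent variable for satisfaction.

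**The concern.** Stability of a correction has meaning only where there was a correction to lose. Under the 3a definition, a patient whose bite was still open when appliances came off is unstable at one year unless it closes late. Relapse and failure to close then share one outcome category.

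Objective 3a is meant to show which retainer regimens and treatment modalities go with a bite that stays closed, and section 2.1 says the literature does not settle which treatment is more stable. If the leading 3a result mixes the two failures, a characteristic that predicts closure can be selected as a predictor of stability even when it has no relation to relapse. Readers would also find one word defined in two ways within one report.

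**Working it through.** **Inputs (protocol).** Section 11.2: 840 enrolled; attrition of 10% to end of treatment and 20% to one year; success 70%; stabilization 50%; 3 patients per practitioner; ICC 5%. Section 11.4.1: a 20-point difference of interest and 110 patients per group.

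**Assumptions not in the protocol.** The share q of not-closed patients who show positive overlap at one year is taken as 0 to 10%. Attrition is taken as equal in closed and not-closed patients.

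**1. Which population was the study sized for?**
- Design effect: 1 + (3 − 1) × 0.05 = 1.10.
- n = 1.96² × p(1 − p) / d² × 1.10. With p = 0.50 and d = 0.05 (the 10% precision read as full interval width), n = 422.6; the table gives 422. The other rows also reproduce: 405.7, 355.0, 270.4 and 152.1 against 406, 355, 271 and 153.
- 422 / 0.70 = 603 (stated 600).
- 600 / (0.9 × 0.8) = 833 and 603 / (0.9 × 0.8) = 837 (stated 840).

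Dividing by 0.70 makes sense only if stability is assessed among closed patients.

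**2. Who enters the main 3a analysis?** The protocol does not say outright. But a not-closed stratum is split off after the final model, so those patients must have been in the data up to then. Success is not among the domains named for the model (retainer regimen, modality, dentofacial, patient, practitioner).

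**3. How many patients are affected?**
- Followed to one year: 840 × 0.9 × 0.8 = 605.
- Closed: 605 × 0.70 = about 423. Not closed: about 181.
- Closed and stable: about 212. Closed and relapsed: about 212.
- With q = 0: stable = 212 / 605 = 35% of all, against 50% of the closed. Unstable = 212 + 181 = 393, and 181 / 393 = 46% of them were not closed at end of treatment.
- With q = 10%: stable = 38% of all. Unstable = about 375, of whom about 163 (44%) were not closed.
- At the literature rates quoted in section 11.2 (success 80%, stability 65%), with q = 0: 121 of 290 unstable, or 42%. At the upper literature figure of 100% stability, every unstable patient would be one who was not closed.

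**4. What can this do to a comparison?** Take two groups with success 80% and 60% (the 20-point difference of section 11.4.1), identical 50% stability once closed, and q = 0.
- All-patient rates: 0.80 × 0.50 = 40% and 0.60 × 0.50 = 30%; odds ratio 1.56.
- Effective size per group: 110 / 1.10 = 100.
- Chance of p < 0.05 = Φ{[0.10 − 1.96 × √(2 × 0.35 × 0.65 / 100)] / √[(0.40 × 0.60 + 0.30 × 0.70) / 100]} = Φ{(0.100 − 0.132) / 0.067} = 0.32.
- With 65% stability once closed, the rates are 52% and 39% and the chance is 0.45.
- Among closed patients alone the rates are equal, so the test rejects at its nominal 5%.

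**The case against.** Much can be said for the plan as written. The protocol never says that 3a is run in all patients; that is inferred from the order of the steps. The 3a sentence refers back to an earlier definition, which could be taken to include the closure condition of section 11.3. Section 3.2 lists success as a factor of interest, and 3a itself ends with an analysis by closure. In the closed stratum the artefact disappears. A statistical analysis plan could also say which analysis leads. Finally, restricting to closed patients conditions on a result of treatment, which can itself distort comparisons between modalities.

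The planned stratum is a real safeguard and limits the harm. It does not remove the defect. The restatement in 3a spells out the outcome and leaves the condition out, the stratum follows a final model with its own retention rule, and nothing says which result answers the objective. The caution about conditioning on closure stands, and is a reason to show an all-patient result too, under an accurate name.

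A reader might infer several stronger points that the documents do not support:
- **That a modality with better closure will simply be reported as more stable.** The same paragraph of the protocol would also show no difference among closed patients.
- **That false significance is close to 70%.** That figure (0.69) needs about 302 per group, an even two-way split of 605 that the protocol does not plan. At its own 110 per group the figure is about 32%.
- **That section 3.2 contradicts section 11.3.** The former gives a rule for reading one patient's photograph, the latter a population. They are compatible.
- **That section 11.3 is wrong to call its measure strict and conservative.** The comparison there can be with the looser assessments of overbite change that follow. The point here does not depend on it.

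**Conclusion.** The point holds as a fault of definition and order in one secondary objective. Section 11.4.2 (3a) omits the closure condition that sections 11.2 and 11.3 use, and as sequenced its main analysis implicitly includes patients whose bite was not closed. At the planning rates these are about 181 of 605 followed patients and about 44% to 46% of those classed as unstable, for late closure between 10% and none.

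The 32% chance of a misleading significant difference is an illustration. It rests on an assumed 80% against 60% contrast in success, equal stability once closed, no late closure and 110 per group. For retainer regimens the distortion arises only if regimen is related to closure, and the protocol gives no figure for that.

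The primary estimates of success and stability and the sample size are not affected.

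**What to change.** In section 11.4.2, objective 3a:
- State that the main analysis (chi-square tests, domain models and final model) is among patients closed at end of active treatment, as in primary objective 2.
- If an all-patient result is kept, report it as positive overbite at one year, not as stability.
- In the stratum not closed at end of treatment, call positive overbite at one year late closure.

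In objective 3b, keep all patients, because the protocol wants to quantify satisfaction among those not treated successfully. Code the predictor in three levels: closed and stable, closed and relapsed, not closed at end of treatment.

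Section 3.2 needs no change, and no data collection changes. The cost is a smaller main 3a analysis: about 423 patients instead of about 605. That matches the 422 planned for a 50% stabilization rate. It is slightly below the 440 (4 × 110) that section 11.4.1 gives for comparing four modalities, so power for that comparison of stability should be restated.

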Of course, the most important outcome for AOB patients may be long-term stability, as closure of AOBs is often challenging to maintain (Appendix B, Figures 8-10)^{3,5}. The literature does point to some factors that may play a role in stability. For example, some clinicians feel that extraction therapy is helpful, as the incisors are tipped backward during space closure, and as they tip back, they also tip downward⁷. This can lead to better stability compared to a situation in which a crowded arch is expanded, tending to cause forward tipping and a more shallow overbite relationship. Other studies suggest that the cessation or altering of oral habits could improve stability, as these could be etiologic factors. For example, there are some reports that crib therapy to stop digit or tongue habits can be relatively stable¹⁶. As mentioned earlier, there are several systematic reviews addressing stability of conventional orthodontics and orthognathic surgery, but they are based on low quality studies³⁻⁶. Currently, there are few studies reporting long-term stability of TAD or clear aligner treatment⁹⁻¹¹. Additionally, only a few case reports describe the effectiveness of different types of retainers after treatment for AOB stability¹⁷⁻¹⁹.

Anterior openbite can be both a functional and cosmetic issue, and correcting it reliably, as well as retaining the correction, has proven to be challenging. Thus, conducting a well-designed study that addresses both treatment and stability may have high impact on the oral health of the public. This study may have significant benefits to future adult AOB patients. It may provide insight into the most effective and stable methods to treat and retain AOBs.

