7 STUDY PROCEDURES/EVALUATIONS

7.1 Study Procedures/Evaluations

Practitioner:

Prior to enrolling patients, the practitioner will complete a Practitioner Characteristics Form which will ascertain types and frequency of typical treatments and retention techniques used to treat adult patients presenting with an AOB.

Patient:

Enrollment. For each patient enrolled, the practitioner will complete an Enrollment Visit Form based upon clinical examination and review of records recording: 1) patients' reasons for seeking treatment; 2) pre-treatment diagnoses (dentofacial characteristics); 3) goals of treatment (practitioner perspective); and 4) treatment plan options, including adjunctive treatment, and treatment plan chosen.

De-identified initial cephalometric x-ray and intra-oral frontal photographs taken prior to treatment initiation will be uploaded for measures of dentofacial characteristics, such as overbite, mandibular plane angle, and incisor angulation (as described above in outcome measures).

At enrollment, after consent, the patient will complete a Patient Enrollment Visit form, which elicits 1) age (from year of birth and date), race/ethnicity, sex, insurance, education; 2) reasons for seeking treatment; 3) treatment recommended as ideal (patient perspective); 4) whether or not accepted ideal recommendation, and if not, why not; and 5) previous orthodontic treatment, if any.

End of active treatment. The practitioner will complete an End of Active Treatment Form based upon clinical examination and review of treatment records recording: 1) any changes in originally accepted treatment plan; 2) treatment result and expected stability outcome; 3) any residual oral habits; 4) patient compliance and adjunctive treatments; 5) current molar relationship; and 6) retention techniques recommended.

De-identified end of active treatment cephalometric x-ray and intra-oral frontal photograph taken in maximum intercuspation will be uploaded for measures of overbite. Practitioner will also obtain an additional intra-oral frontal photograph taken with the incisors slightly apart and upload the de-identified photo for measures of overbite. The practitioner will also measure the height of the right maxillary central incisor using the provided metal ruler.

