11.4.2 Proposed Secondary Analyses

Analysis plan for Secondary Objectives:

Secondary objective #1a will examine how dentofacial, as well as patient and practitioner characteristics influence treatment recommendations suggested by the orthodontists. The association of each of the dentofacial, patient and practitioner characteristics specified below with different treatment recommendations will be ascertained using a chi-square test for categorical variables and either t-test or Wilcoxon rank-sum test (nonparametric equivalent). Dentofacial characteristics: profile, molar classification, maxillary crowding, mandibular crowding, posterior cross-bite, facial pattern. Patient characteristics: age, sex, race/ethnicity, insurance, education, treatment goals. Practitioner characteristics: age, sex, race/ethnicity, year received orthodontic training. For each domain of the three domains, namely, dentofacial, patient and practitioner characteristics, characteristics with $p < 0.2$ will be entered in the model, retained if $p < 0.1$. Final Generalized Estimating Equations (GEE) regression model (adjust for clustering within practice) will start with those $p < 0.1$ for each domain, and retained if $p < 0.05$ for final analysis ascertaining how dentofacial, as well as patient and practitioner characteristics influence treatment recommendations (extraction, then surgical component, fixed appliances, removable aligners, TADs).

Secondary objective #1b will examine how dentofacial, as well as patient, practitioner, characteristics influence whether or not treatment recommendations suggested by the orthodontists are accepted by the patients. Method described above will be repeated for acceptance of recommendations. Separate analyses, i.e., stratum specific, will be performed for recommendations involving extraction and those not. Of interest (though not a primary objective or specific hypothesis to be tested) within this secondary objective is exploring what factors influence whether or not patients accept treatment recommendations involving an extraction or surgical component.

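### The retainer comparison in objective 3a names neither millimetric overbite at appliance removal nor residual oral habits as covariates, so it is open to confounding by how secure the closure was

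*Protocol*

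**What the plan says.** Objective #3a in protocol section 11.4.2 has two steps. First, "type of retainer (Hawley, Essix, bonded) and frequency of use prescribed (full or part-time) with treatment stability will be assessed with chi-square test". Then the domains are modelled: "The treatment modalities (extraction, then surgery, fixed appliances, removable aligners, or TADs), dentofacial, patient and practitioner characteristics described above, will be used to ascertain their" link to stability, and a retainer domain is added. Within a domain, entry is at p < 0.2 and retention at p < 0.1. In the combined model, entry is at p < 0.1 and retention at p < 0.05. No term is forced in. Further analyses are stratified by extraction and by whether the bite was closed at the end of active treatment.

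The lists that 3a points back to stand under objective #1a: "Dentofacial characteristics: profile, molar classification, maxillary crowding, mandibular crowding, posterior cross-bite, facial pattern" and "Patient characteristics: age, sex, race/ethnicity, insurance, education, treatment goals". The practitioner list is age, sex, race/ethnicity and year of orthodontic training.

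Section 3.2, on the one-year outcomes, lists end-of-treatment success and, among dentofacial characteristics, the magnitude of overbite in millimetres. It gives no time point for that magnitude.

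The data exist. On overbite at removal and at follow-up, section 3.2 says: "Using this measurement, along with the end-of-treatment and follow-up photos, the overbite can be calculated at each time point". Section 7.1 has the End of Active Treatment Form record "2) treatment result and expected stability outcome; 3) any residual oral habits; 4) patient compliance and adjunctive treatments; 5) current molar relationship", followed by the retention techniques recommended. Section 2.1 says: "Other studies suggest that the cessation or altering of oral habits could improve stability, as these could be etiologic factors".

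**The concern.** Stability means positive incisal overlap at one year, and section 11.3 takes its primary measure among patients already closed. For them, overlap at appliance removal is the starting value of the outcome. A bare overlap and a deep one count the same in the closed stratum, although the first has less room to relapse before it is classed as unstable.

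Section 4 says that the study does not influence treatment, so retention is chosen by the practitioner. Final overlap and any persisting habit are observable at the visit where that choice is recorded. Either could plausibly affect both the regimen and relapse. If stricter retention went to less secure closures, it would look less stable even with no effect of its own. The variables that would address this are collected, but 11.4.2 does not name them as candidates. The opening chi-squares adjust for nothing.

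**Working it through.** **1. Covariates, set side by side**

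| Variable | Collected at removal? | 3.2, factors for stability | 11.4.2 lists used by 3a |
|---|---|---|---|
| Overbite, mm | Yes (3.2, 6.3.1, Appendix C) | Magnitude listed, no time point | Not listed |
| Closed / not closed | Yes | Listed | Stratification only |
| Residual oral habits | Yes (7.1) | Not listed | Not listed |

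Sections 3.2 and 11.4.2 disagree on overbite magnitude. Habits appear in neither list.

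**2. The plan's own yardstick**

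Section 11.4.1 asks for 110 patients per group to detect 20 points (80% power, 5% level, ICC 5%). The base rate is not stated. Taking 40% against 60%, two-sided, pooled variance:

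- n = [1.96·√(2·0.5·0.5) + 0.842·√(0.4·0.6 + 0.6·0.4)]² / 0.20² ≈ 97.
- Design effect 1 + (m − 1)·0.05 is 1.10 at 3 patients per practitioner and 1.15 at 4.
- 97 × 1.10 = 106.7 and 97 × 1.15 = 111.5, so 110 reproduces.

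**3. Numbers available**

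840 enrolled × 0.9 (retained to end of treatment) × 0.7 (closed) × 0.8 (retained to one year) ≈ 423 closed patients with one-year data. Two extra terms are affordable.

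**4. Illustration by hand (all values assumed)**

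Take closed patients only, half with a fragile closure, and no true regimen effect. Stability is 80% if solid and 50% if fragile. Full-time wear is prescribed to 70% of fragile and 30% of solid closures.

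- Full-time: 0.7 × 0.50 + 0.3 × 0.80 = 0.59.
- Part-time: 0.3 × 0.50 + 0.7 × 0.80 = 0.71.
- False difference: −12 points. At 110 per group and design effect 1.10 (100 effective), the chance of p < 0.05 is about 43%.

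Varying stability from 90/70% to 70/30% (solid/fragile) and full-time prescribing from 60/40% to 80/20% (fragile/solid) gives −4 to −24 points. The chance of p < 0.05 then runs from about 10% to 93%. Adjusting for fragility gives 0 by construction.

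**5. Simulation on a continuous scale (all values assumed)**

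Overbite at removal and at one year are bivariate normal with correlation rho. The odds of full-time wear rise by exp(0.5) or exp(1.0) per SD shallower overbite. There is no regimen effect. The table shows full-time minus part-time stability in points, for the weaker and stronger prescribing slope.

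| rho | Assumptions hold within the analysed group, 70% stable | Whole cohort, restricted to 70% closed, 70% of them stable | Same, 50% of them stable |
|---|---|---|---|
| 0.3 | −5.0 / −8.7 | −2.3 / −4.3 | −2.8 / −5.1 |
| 0.5 | −8.3 / −14.5 | −4.0 / −7.4 | −5.0 / −9.0 |
| 0.7 | −11.6 / −20.5 | −6.0 / −11.0 | −7.5 / −13.7 |

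Restricting to closed patients roughly halves the false difference and does not remove it.

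**6. Precision**

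For 50% against 70% stable, 100 effective per group and an assumed rho of 0.5, simulated power rises from about 83% unadjusted to 89% adjusted.

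**The case against.** - **Overbite at removal is not absent.** It enters 3a through the closed / not closed strata, and section 3.2 names overbite magnitude for stability. A reader might infer that the plan ignores it altogether, and that would be wrong. The gap is narrower: the degree of overlap is missing from the 11.4.2 lists, and 3.2 gives no time point. Habits are in neither list.
- **Confounding is not shown.** A reader might infer that the retainer results are confounded, or will point the wrong way. No section says how retainers are chosen. Section 7.1 has practitioners report their typical retention techniques before enrolling anyone. If choice mostly follows habit of practice, patient-level confounding is weaker. The objective also speaks of association and makes no causal claim. This stands against asserting bias as fact. It does not stand against prespecifying plausible common causes that are already measured.
- **The bias figures are assumed throughout.** Correlation, slope and direction of prescribing are not in the protocol. The upper end, close to the 20-point target, is the extreme corner of the grid. This stands.
- **Precision is easily overstated.** The factor 1 − rho², a 25% variance cut at rho 0.5, is for a continuous outcome. Stability is binary and the gain is smaller.
- **Adjustment sets may be left to the SAP.** That would answer a silent protocol. This one names its lists and its selection rule, and the lists conflict with section 3.2.

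**Conclusion.** The point holds in a limited form. The covariate lists that 3a relies on omit millimetric overbite at removal and residual oral habits, although both are collected and the background section ties habits to stability. Section 11.4.2 also conflicts with 3.2 on overbite magnitude. The retainer comparison among closed patients is therefore open to confounding by how secure the closure was. The protocol does not allow the size to be determined.

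On the assumed grid (rho 0.3 to 0.7, odds ratio exp(0.5) to exp(1.0) per SD, no true effect), the false difference is about 2 to 14 points under whole-cohort assumptions with restriction to the closed. It is 5 to 21 points if the assumptions hold within the analysed group at 70% stable. Against a 20-point target, the middle and upper values matter. The primary objectives are untouched. This is a change the plan should make to a secondary objective.

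**What to change.** In section 11.4.2, objective #3a:

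- Name overbite at appliance removal (continuous, mm, from the Appendix C photographs, the method also used at one year) and residual oral habits (End of Active Treatment Form) as prespecified covariates. Keep both regardless of p-value in the GEE model for retainer regimen among patients closed at end of treatment.
- Take the retainer conclusion from that model, and label the chi-squares as unadjusted description.
- Leave the two terms out of the treatment-modality contrasts, where they lie downstream of the exposure.
- Reconcile section 3.2 with the 11.4.2 lists by stating the time point of the overbite covariate.

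The cost is wording, two extra model terms and a separate model for modality. All variables are already collected.
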